This study will use a single group repeated-measures design to address the following Specific Aims:

Aim #1: To determine the feasibility of a 6-week UZIT intervention in community-dwelling adults with PH. Feasibility will be determined by 1) recruitment rate (>40% recruited from those approached), 2) enrollment (\geq two participants /month) (Carter et al., 2013; Uebelacker et al., 2010), 3) home practice (\geq 1/week), and 4) retention rate (\geq 70% of participants remaining at study completion). We will also explore UZIT interventionists' perception about study feasibility.

Hypothesis 1: UZIT will meet feasibility targets for community-dwelling adults with PH.

Aim #2: To determine the acceptability of UZIT among community-dwelling adults with PH for symptom management. Acceptability will be determined by participants' evaluation of the UZIT program (composite mean System Usability Scale score > 5, scale 1-7), (Brooke, 1986) and session completion rate (at least 5 of 6 sessions [83% attendance]) (Campo et al., 2013; Cohen et al., 2007; Lee et al., 2010; Lengacher et al., 2011; Palumbo, Wu, Shaner-McRae, Rambur, & McIntosh, 2012) by the participants retained at the study end. An exploratory sub-aim (Aim 2-A) is to determine what components of the UZIT program are preferred by adults with PH. We will also explore UZIT interventionists' perception about participants' acceptability of the UZIT intervention.

Hypothesis 2: UZIT will meet acceptability standards among community-dwelling adults with PH.

Aim #3: To explore the preliminary efficacy of UZIT intervention.

Aim #3a: To explore the preliminary efficacy of weekly UZIT sessions on dyspnea, pain, fatigue and anxiety.

Aim #3b: To explore the preliminary efficacy of a 6-week UZIT program on PH-related symptoms and HrQoL.

Hypothesis 3a: Patients will report reduced presence and intensity of dyspnea, pain, fatigue and anxiety after each UZIT session.

Hypothesis 3b: Patients will report a decrease in the presence, severity, and activity interference for PH-related symptoms and improvement in HrQoL after UZIT program compared to baseline.

III. Background and Rationale

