This is an important foundational study to establish feasibility and acceptability and, potentially, to identify needed refinements, in integrative therapies for symptom management in complex chronic, life-limiting cardio-pulmonary disease. Once UZIT is established as feasible and acceptable for PH patients, future research will focus on testing the efficacy and effectiveness of UZIT to reduce symptom burden and promote HRQOL for persons with complex chronic, life-limiting cardio-pulmonary disease. Additional studies will include analysis of cost and health care utilization outcomes. The long-term goal of this program of research is to advance knowledge and evidence-based application of integrative therapies to manage symptoms and promote quality of life for persons with complex chronic, life-limiting cardiopulmonary conditions.

III. Procedures

A. Research Design

This feasibility and acceptability study will use a pre/post intervention (6-weeks UZIT program) mixed-method design with repeated (weekly) measures of a single cohort of patients with PH. We will also explore preliminary efficacy testing to construct sample size estimates for future randomized control trials. Patients will serve as their controls.

B. Sample

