We will enroll 20 patients from two PH clinics within the Ohio State University Wexner Medical Center (OSUWMC). Patients with PH condition related to the cardiac cause are managed at the OSU Cardiology clinic located at the Ross Heart Hospital. Patients with PH condition related to other causes are managed at the OSU Pulmonary clinic at Martha Morehouse. These inter-professional clinics provide access to a patient population with diverse race/ ethnicity, sex, and age. Overall, the OSUWMC PH Program manages approximately 350 PH patients each year and receives referrals for 50 new patients per year. PH patients' characteristics are similar to the U.S. data registry with a mean age of 55.8 years, 75% female, and 79% Caucasian. Patients at all stages of PH disease are followed for routine clinic appointments at 6-month intervals or more frequently if clinically indicated. Newly diagnosed patients are seen by PH specialists at 2-4 weeks interval for the first six months due to frequent monitoring and medication adjustments. All eligible patients managed at both PH clinics at OSUWMC will be invited to participate. Patients in both clinics receive standard medical treatments according to institutional and national clinical practice guidelines (McLaughlin et al., 2009; The Ohio State University Wexner Medical Center, 2014).

Sample.

Twenty convenience sample of community-dwelling adults with PH will be recruited for this study. Inclusion criteria are: 1) confirmed diagnosis of PH in the past, 2) age \geq 18 years, (children typically have different etiologies, and often require parent involvement in symptom management), 3) ability to ambulate independently, 4) New York Heart Association functional classification II/III, and 5) willingness to participate in the entire 6-8 weeks study. Exclusion criteria are 1) known allergies to essential oils (lavender, lemon, or peppermint), 2) Asthma condition, 3) psychiatric illness requiring hospitalization within the last year per self-report or medical record, 4) self-reported pregnancy, 5) on-going participation in mind-body integrative therapy, and 6) inability to read/write English (to complete questionnaires).

Sample Size and Statistical Power.

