The primary purposes of this study are to establish feasibility and acceptability of the UZIT intervention. A descriptive analysis will be applied. Pilot feasibility and acceptability studies of integrative behavioral approaches similar to the one proposed here generally include 6-19 participants (Cohen et al., 2007; Freedenberg, Thomas, & Friedmann, 2015; Lengacher et al., 2011; Palumbo, Wu, Shaner-McRae, Rambur, & McIntosh, 2012; Uebelacker et al., 2010; Yeh et al., 2010). With regards to preliminary efficacy outcomes of PH-related symptoms and PH-related HRQoL, we estimated statistical power. Power analysis using two-sided paired tests (*t*-tests for continuous and McNemar test for dichotomous/categorical outcomes) indicates that a sample size of 15 has sufficient power (≥ 0.8) to detect large effect size (standardized mean difference of 0.78 or greater for continuous outcomes; odds ratio of 7 or greater for dichotomous/categorical outcomes, assuming that proportion of discordant pairs is 0.6) with a significance level of 0.05. Therefore, small to medium effect sizes will not be detected as statistically significant in this study. As a pilot study to generate information on preliminary efficacy, we will not rely on statistical significance, but rather on clinical differences. Anticipating 10-15% attrition rate over a 6-8 week behavioral intervention study (Carter et al., 2013; Grossman et al., 2010), we will enroll 20 participants to achieve a final minimum sample of 15.

C. Measurement / Instrumentation

Table 1 outlines the data collection timeline. Participants will provide demographic data at enrollment. The PI's preliminary work demonstrated that PH patients were able to complete four questionnaires in outpatient clinic settings within 15-minutes without undue burden. One hundred and eleven participants of 115 enrolled (96.5%) completed all four questionnaires without difficulty.

Table 1: Data Collection Timeline

Measurement	Study AIMS	Week 0	Week 1	Week 2	Week 3	Week 4	Week 5	Week 6
Consent		X						
Demographics		X						
UZIT Intervention			X	X	X	X	X	X
Phone Call			X	X	X	X	X	X
Diary Record	2, 3b		X	X	X	X	X	X
Field Notes	2		X	X	X	X	X	X
Debriefing (P)	2				X			X
Debriefing (I)	2, F		X	X		X	X	
Session Video Recording	2, F		X	X	X	X	X	X
Acceptability Survey	2							X
PAHSS	3b		X					X
Dyspnea, Pain, Fatigue, Anxiety	3a		X	X	X	X	X	X
Manipulation Check	F						X	
Enactment Check	F						X	
CAMPHOR	3b		X					X

Data Collection Instruments

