The UZIT Interventionists questionnaire will also solicit interventionists' perception about UZIT feasibility, patients' acceptability of UZIT intervention, and UZIT fidelity. Because interventionists had been closely involved in the creation and refinement of the UZIT intervention protocol and fidelity training throughout the course of study period, series of questions in this questionnaire will include these 3 aspects of query (please see attached). Interventionists' audio recorded comments will be transcribed verbatim, coded and categorized for common themes using NVivo qualitative data analysis program.

D. Detailed study procedures

Intervention.

Individual, one-to-one UZIT sessions will be delivered by experienced therapists who are trained and certified in UZIT curriculum and training protocol (4 months coursework + 6-8 hours/week practice+50 hours clinical practicum). Individual rather than group intervention delivery reduces distractions and the social influences of a peer group. Private UZIT sessions are also more conducive to tailored treatment and allow for a more accurate symptoms query. A competency check-off list will be required of all UZIT interventionists before delivering study intervention. At least two experienced, UZIT-trained therapists will be trained in the study intervention delivery according to the research protocol. Sessions will be arranged at a convenient time for patient and therapist and conducted at the OSU Integrative Medicine outpatient facility in Columbus, Ohio. The facility is easily accessible and conveniently located close to the main medical facility; parking is free. Patients will participate in a total of 6 visits lasting approximately 1 to 1.5 hours per visit to be scheduled within an 8-week period. Participants will receive an incentive of \$30.00 in gift certificates for the entire study, distributed in \$5 increments at the end of each visit. This amount is considered reasonable because the study intervention (personal UZIT sessions) has an estimated market value of \$100.00 per session and will be provided at no cost to participants.

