available through the OSU Center for Clinical and Translational Science; or (4) patients with confirmed PH diagnosis will be screened by clinic staff during routine PH clinic visits for potential study eligibility. When PH clinic patients are identified as potentially eligible, clinic staff will provide a study brochure and inquire whether the patient would like to learn more about the study. If a patient indicates interest in the study, s/he will be approached by the study PI for consent. Clinic staff will follow a verbal script in seeking patients' interest. Research staff will follow a verbal script in describing general information about the study. The consenting process will include further discussion about the study protocol and participation including risks and benefits with sufficient time to address all questions. After consent, the initial study visit will be scheduled.

Potential Risks.

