Aim 3A: To explore the preliminary efficacy of weekly UZIT sessions on dyspnea, pain, fatigue, and anxiety. Symptoms of dyspnea, pain, fatigue, and anxiety (symptom intensity) will be assessed in response to each UZIT session. We will plot the weekly visit rating of symptoms (dyspnea, pain, fatigue and anxiety) trajectory pattern from week 1 through week 6 for each participant and by biological variables (e.g. age groups, sex, and NYHA classification). Mixed effect modeling for repeated measures will be used to model the change over time. Estimates derived from mixed effect modeling will be more accurate by accounting for within-subject correlation. It also has the advantage of the most efficient use of data. Estimates are derived from all available data, not just data from completers.

Aim 3B: To explore the preliminary efficacy of 6-week UZIT program on PH-related symptoms and HRQoL. We will compare pre-and post-differences in composite symptoms' presence and severity (PAHSS) and HRQoL (CAMPHOR domains) using McNemar tests for paired proportions and dependent *t*-tests for paired means. As a pilot study to generate information on preliminary efficacy, we will rely on clinical differences. The point estimates and effect sizes from this pilot study will guide the sample size calculation for future larger scale study (efficacy and effectiveness). We will primarily report summary statistics on proportions and 95% confidence intervals at each time point. We will also determine the correlation between changes in PAHSS and CAMPHOR scores with a dose of home practice (minutes/week) to indicate a dose-effect relationship. Furthermore, the frequency and the amount of home practice can serve as an indicator of participants' acceptability of the UZIT program.

IV. Bibliography

Include a reference list of literature cited to support the protocol statement.

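### Week 1 to Week 6 change (Aim 3b and the Aim 3a trajectory) is uncontrolled: calling patients their own controls does not remove drift or background treatment changes, and no explicit plan records those changes

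*Combined protocol and SAP*

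**What the plan says.** **Design.** Section II (Objectives) says "This study will use a single group repeated-measures design to address the following Specific Aims". Section III.A (Research Design) describes a pre/post study of one cohort with weekly measures and adds "Patients will serve as their controls".

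**Timing of outcomes.** Section C says "Participants will provide demographic data at enrollment". In Table 1, Week 0 is marked for consent and demographics only. PAHSS and CAMPHOR are marked at Weeks 1 and 6. The dyspnea, pain, fatigue and anxiety ratings and the diary run from Week 1, the week of the first session. No measurement is scheduled after Week 6.

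**Interval before treatment.** Under Recruitment: "After consent, the initial study visit will be scheduled". The length of that gap is not given. The treatment period is given: "Patients will participate in a total of 6 visits lasting approximately 1 to 1.5 hours per visit to be scheduled within an 8-week period".

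**Background treatment.** Section B says of the clinics: "Newly diagnosed patients are seen by PH specialists at 2-4 weeks interval for the first six months due to frequent monitoring and medication adjustments". The eligibility list asks for a past confirmed diagnosis. It sets no minimum time since diagnosis and no condition on current therapy. Table 1 has no row for concurrent treatment.

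**Use of the result.** Section E, Aim 3B compares Week 1 with Week 6 by paired tests and states "The point estimates and effect sizes from this pilot study will guide the sample size calculation for future larger scale study".

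**The concern.** A comparison of each patient with himself or herself removes whatever is constant in that patient. To separate the programme from the passage of time it would also need outcome data from a period without the programme. Table 1 has none: there is a single value before the first session, home practice fills the time between sessions, and there is no follow-up.

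Three rival explanations for a Week 1 to Week 6 change therefore remain open: natural drift of the disease, regression to the mean, and changes in PH treatment made during the study. The third is concrete here, because the protocol itself describes a group of eligible patients whose medication is often adjusted. The background section criticises an earlier retrospective chart review of integrative therapy for ignoring drug effects and for not monitoring fidelity. This plan deals with fidelity in detail, but its internal validity section does not mention drug effects.

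At stake is what Aim 3b can conclude, and the effect size handed to the next trial.

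**Working it through.** **1. The plan's own figure.** Inputs from Sample Size and Statistical Power: n = 15, standardized paired difference 0.78, two-sided alpha 0.05. Noncentrality = 0.78 × √15 = 3.02, df = 14, critical t = 2.145. Power from the noncentral t distribution is 0.802, which agrees with the stated 0.8 or more. The 0.78 is in SDs of *change*.

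**2. Which outcomes have an untreated interval.**

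| Outcome | Before session 1 | Later | Untreated interval |
|---|---|---|---|
| PAHSS | Week 1 only | Week 6 | none |
| CAMPHOR | Week 1 only | Week 6 | none |
| Four symptom ratings, weekly trajectory | Week 1 only | Weeks 2–6 | none |
| Four symptom ratings, within a session | start of each session | end of the same session | not needed for multi-week drift |

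The last row follows from the stated purpose of measuring immediate change after each session. Over 1 to 1.5 hours, slow drift or a medication change is not a credible rival. Rest, attention and expectation are.

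**3. Opportunity for treatment change.** At one specialist visit every 2–4 weeks, a newly diagnosed participant has 8/4 = 2 to 8/2 = 4 visits within the 8-week window. The documents do not say how many such patients will enrol.

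**4. What drift would do.** The drift sizes are assumed, since the documents give none. Same test, n = 15, drift in SDs of change:

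| Drift | No true effect, drift favourable: P(significant favourable result) | True effect 0.78, drift adverse: power |
|---|---|---|
| 0 | 2.5% | 80% |
| 0.1 | 5.5% | 69% (net 0.68) |
| 0.2 | 10.8% | 55% (net 0.58) |
| 0.3 | 19.0% | 41% (net 0.48) |

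The effect size passed on is shifted whether or not a p-value is used. Required sample size goes as 1/d². If 0.2 of an observed 0.78 were drift, a trial sized on 0.78 would need (0.78/0.58)² = 1.8 times as many patients.

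**5. What a Week 0 measurement could and could not do.**
- *As an adjusted test:* take (Week 6 − Week 1) − (Week 1 − Week 0). With equal spread of the two changes and correlation ρ between them, the contrast has √(2(1−ρ)) times the SD of the simple change. For ρ from −0.5 to 0 (assumed) the factor is 1.73 to 1.41, and 0.78 becomes 0.45 to 0.55. Power at n = 15 is 0.37 to 0.51. At ρ = −0.5, 80% power needs 41 completers.
- *As a noise level for six-week change:* the SD of change is √(2(1−r)) score SDs. Suppose the CAMPHOR test-retest correlations in Section C (0.86–0.92, interval not stated) applied to the short Week 0–1 gap. That gives 0.53–0.40. With r = 0.6–0.7 over six weeks (assumed) it is 0.89–0.77. The short gap would understate six-week noise by about a third to a half.

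**The case against.** The strongest reply is that the plan already limits its claims. Efficacy is secondary and exploratory. The sample size section disclaims reliance on significance. The single-cohort pre/post design is stated openly next to the own-control sentence, which is common shorthand for a paired comparison, and randomized trials are announced as the next step. This stands, and it is why the point is modest. It does not dispose of the point, because a shift in the point estimate remains without a p-value and the plan passes that estimate on.

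A reader might also infer more than the documents support:

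- *That no pre/post change in this study is interpretable.* Within-session change in Aim 3a is little exposed to drift or medication changes (step 2).
- *That the bias amounts to some fixed share of 0.78, up to about half.* That would require a sample enrolled about 1 SD worse than its population mean and an assumed six-week correlation of 0.6–0.7. The eligibility list sets no symptom or quality-of-life threshold, and NYHA class II/III is its only severity criterion. Regression expressed in score SDs also cannot be set directly against 0.78, which is in SDs of change.
- *That the bias must favour the programme.* The protocol describes PH as rapidly progressive, so drift may be adverse and hide a benefit.
- *That nothing about other treatment is captured.* The diary asks how other symptoms are managed and is linked to Aim 3b in Table 1; its form is not in the text available. The fair statement is that no explicit plan to record PH-treatment changes is given.

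**Conclusion.** The point holds for Aim 3b (PAHSS and CAMPHOR, Week 1 to Week 6) and for the Week 1–6 symptom trajectory in Aim 3a. For these, the own-control sentence promises more than the design gives: stable between-patient differences are removed, while drift, regression to the mean and co-treatment are not. The direction is open and the size cannot be derived from the documents. The figures in step 4 rest on assumed drift and show sensitivity only.

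Feasibility and acceptability, the primary aims, are untouched. This is a cheap improvement to the wording, recording and reporting of a secondary aim. A reader might conclude that a Week 0 measurement would turn the study into a controlled one. It would not: the gap is undefined and probably much shorter than the treatment period, it cannot capture treatment changes during Weeks 1–6, and the adjusted contrast lacks power at this sample size.

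**What to change.** 1. In Section III.A, replace the own-control sentence with a statement that Aim 3b and the weekly trajectory describe *uncontrolled within-patient change*.
2. Add one question on PH-treatment changes to the weekly call already in Table 1, and record time since diagnosis at enrolment.
3. In Section E, report the Aim 3b change for all participants, and with and without those whose PH treatment changed. Present this descriptively.
4. Where the effect sizes are said to guide the next sample size, state that they are uncontrolled and may be biased in either direction.
5. Optional: give PAHSS and CAMPHOR at the Week 0 contact, record the days to session 1, and report the Week 0–1 change descriptively. Do not use it as an adjusted test or as the noise level for six-week change.

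**Cost.** One call question per week, one enrolment item, and a few minutes of questionnaires if Week 0 is used. With 15–20 participants the with/without groups may be very small, so the summary can show whether the result depends on a few patients but cannot test it.

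### The stated McNemar power of at least 0.8 with 15 pairs does not follow from its inputs, which give about 0.54 to 0.69 two-sided

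*Combined protocol and SAP*

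**What the plan says.** Section III.B, Sample Size and Statistical Power, introduces the calculation as "Power analysis using two-sided paired tests", with t-tests for continuous outcomes and the "McNemar test for dichotomous/categorical outcomes". It concludes that "a sample size of 15 has sufficient power" (0.8 or more, significance level 0.05) for a standardized mean difference of at least 0.78, or for an "odds ratio of 7 or greater for dichotomous/categorical outcomes, assuming that proportion of discordant pairs is 0.6". It names no formula, software or McNemar version.

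The same section limits the weight of this: small to medium effects will not reach significance, and "we will not rely on statistical significance, but rather on clinical differences". Enrolment is 20, so that at least 15 remain: "Anticipating 10-15% attrition rate over a 6-8 week behavioral intervention study".

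Section III.E, Aim 3B, plans "McNemar tests for paired proportions" for the before-and-after comparison, alongside paired t-tests. It also says: "We will primarily report summary statistics on proportions and 95% confidence intervals at each time point".

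**The concern.** McNemar's test uses only the discordant pairs. With 15 pairs and 0.6 discordant, about 9 are expected to be informative. A two-sided exact test on 9 needs at least 8 in the same direction, so power of 0.8 at an odds ratio of 7 looks too high.

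What is at stake is how a non-significant McNemar result would be read. A reader who trusts the stated figure would think that an odds ratio of 7 had at most a 20% chance of being missed, and could take a null result as fair evidence against a large effect. The plan's own caution covers only small to medium effects, so it does not correct that reading.

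**Working it through.** **Inputs, all from Section III.B.** n = 15 pairs; two-sided α = 0.05; odds ratio 7; discordant proportion 0.6; claimed power at least 0.8.

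Discordant cells: p₁₀ = 0.6 × 7/8 = 0.525; p₀₁ = 0.6 × 1/8 = 0.075; difference d = 0.45. Expected discordant pairs: 15 × 0.6 = 9.

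**Companion figure.** For the paired t-test with standardized difference 0.78, the noncentrality is 0.78 × √15 = 3.02 on 14 degrees of freedom, and two-sided power is 0.802. That half reproduces.

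**McNemar, normal approximation with the null variance.**

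z = (√n·d − 1.96·√0.6) / √(0.6 − d²) = (1.743 − 1.518) / √0.3975 = 0.225 / 0.630 = 0.36, so power is 0.64.

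**McNemar, full enumeration.** The number of discordant pairs is m ~ Bin(15, 0.6). Given m, the count in the favourable direction is Bin(m, 7/8). Reject when the two-sided p ≤ 0.05 and sum over m. For the exact test, the main terms are:

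| m | P(m) | Needed in one direction | Power given m | Contribution |
|---|---|---|---|---|
| 5 or fewer | 0.034 | cannot reject | 0 | 0 |
| 6 | 0.061 | 6 | 0.449 | 0.027 |
| 7 | 0.118 | 7 | 0.393 | 0.046 |
| 8 | 0.177 | 8 | 0.344 | 0.061 |
| 9 | 0.207 | 8 | 0.687 | 0.142 |
| 10 | 0.186 | 9 | 0.639 | 0.119 |
| 11 | 0.127 | 10 | 0.592 | 0.075 |
| 12 to 15 | 0.091 | 10, 11, 12, 12 | 0.75 to 0.89 | 0.073 |

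The total is 0.543. The same sum with the other rejection rules gives the rest of the enumerated column below. A simulation of 400,000 trials agrees (exact 0.544, mid-p 0.660, uncorrected 0.664).

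**Conditional shortcuts, m fixed at 9.** Exact: P(8 or 9 of 9) = 9 × (7/8)⁸ × (1/8) + (7/8)⁹ = 0.387 + 0.301 = 0.687. Normal: (3 × 0.375 − 1.96 × 0.5) / √(7/64) = 0.44, so power is 0.67.

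| Two-sided version | Power, n = 15 | n for 0.80 at OR 7 | OR for 0.80 at n = 15 |
|---|---|---|---|
| Exact | 0.543 | 24 | 18.0 |
| Continuity-corrected | 0.543 | 24 | 18.0 |
| Normal approximation | 0.639 | 21 | 13.5 |
| Mid-p | 0.659 | 20 | 11.4 |
| Uncorrected chi-square | 0.663 | 20 | 11.1 |
| Conditional normal, m = 9 | 0.669 | 19 | 9.8 to 9.9 |
| Conditional exact, m = 9 | 0.687 | – | 9.8 to 9.9 |

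The last two rows are shortcuts, because m is not fixed in practice. The tests themselves stop at 0.66.

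**More completers.** Attrition of 10-15% from 20 leaves 18 or 17. Power at 17 and 18 is 0.624 and 0.659 (exact), 0.724 and 0.751 (mid-p), 0.725 and 0.752 (uncorrected), and 0.745 and 0.777 (conditional normal). With all 20 analysed it is 0.721 (exact) or 0.800 (mid-p or uncorrected).

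**More discordance.** Keeping an odds ratio of 7 and 15 pairs, power of 0.80 needs a discordant proportion of about 0.79 (mid-p, uncorrected or normal approximation) or 0.92 (exact), against the 0.6 assumed.

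**The case against.** **A looser planning formula comes close.** A two-sided normal approximation that uses only the alternative variance gives z = 0.45 × √15 / √0.3975 − 1.96 = 0.80, so power is 0.789. It reaches 0.80 at an odds ratio of about 7.2, and gives 0.84 to 0.86 at 17 to 18 completers. This may be where the figure came from. It is not McNemar's statistic, which uses the null variance, and it is still short of 0.8 at n = 15. The test it describes, when enumerated, has power 0.758 and a type I error of 0.073. An arcsine approximation gives 0.72.

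**A one-sided calculation could also be the source.** At one-sided 0.05 the uncorrected test gives 0.813 and the conditional normal shortcut 0.820, although the exact test gives only 0.662. The plan says two-sided.

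**The 0.6 might mean the larger discordant cell.** The wording does not read that way. If it did, the enumerated McNemar tests would still give only 0.63 to 0.73 at n = 15.

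**Little depends on the figure.** This is the strongest point, and it stands as a limit on importance. The primary aims are feasibility and acceptability, analysed descriptively. The plan disclaims reliance on significance, reports mainly proportions with confidence intervals, and sizes the later study from point estimates and effect sizes, not from this power figure. The target of 15 is separately supported by the correct t-test calculation. None of this makes the clause true, and McNemar tests are still planned.

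**Conclusion.** The McNemar power claim is wrong as written. On the plan's own inputs, two-sided power with 15 pairs is 0.54 to 0.66 for the tests themselves and at most 0.69 with the conditional shortcuts. That is 11 to 26 percentage points below the stated 0.8. The chance of missing an odds ratio of 7 is 34% to 46% for the tests, or 31% at the most favourable shortcut. The 17 to 18 completers expected under the plan's attrition do not close the gap (0.62 to 0.78).

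The only thing the plan leaves open is the McNemar version, and the range covers the usual choices. How the 0.8 was obtained cannot be determined from the documents. The effect is confined to the dichotomous outcomes of exploratory Aim 3B. It should be corrected, but it does not threaten the study's primary conclusions.

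**What to change.** Name the McNemar version to be used in Aim 3B and restate the dichotomous clause to match. Possible wording: *For dichotomous outcomes, assuming 0.6 discordant pairs, 15 pairs give two-sided power of about 0.66 (mid-p or uncorrected McNemar test) to detect an odds ratio of 7; 80% power requires an odds ratio of about 11.* If the exact test is chosen, the figures are 0.54 and about 18.

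Leave the t-test figure, the caution about small to medium effects, the enrolment of 20 and the 70% retention criterion as they are. The cost is one clause and a less favourable power figure. No aim, analysis, sample size or decision rule changes.

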The study PI will observe and describe any relevant impressions during the UZIT session; and document semi-structured debriefing interviews at the end of the session with patients or therapist independently. Post session debriefing will be conducted with participants at the end of week #3 and week #6 and with interventionist at the end of other sessions (#1, #2, #4, and #5) to ensure adherence to the research protocol. Patients will be asked to rate their preference for each UZIT component ("like" most to least). Exit interview questions will be included at the end of UZIT program.

Home Practice Diary.

Participants will rate the intensity of dyspnea, pain, fatigue, and anxiety and record each UZIT modality used (Table 10). They will describe how they manage other symptoms and the amount of time (minutes) spent each day practicing each component. Participants will be reminded to complete diary entries using paper format prior to each UZIT session.

Pulmonary Arterial Hypertension Symptoms Severity Scale (PAHSS).

PAHSS is specifically designed to assess presence and intensity of 17 common symptoms identified from a sample of PAH patients (Matura et al., 2014), which respondents rate in severity from "0" to "10" (Table 11). This tool demonstrated construct validity with SF-36 ($\alpha = .84$) and the Profile of Mood States ($\alpha = .70$).

Cambridge Pulmonary Outcome Review (CAMPHOR).

CAMPHOR is a 45 item, PH-specific quality of life tool that measures everyday experiences of PH patients. It measures multiple elements of each domain (symptoms, functional activities, and QOL perception) with simple and easy-to-understand phrasing (Table

12). The CAMPHOR demonstrated good internal consistency (Cronbach α = 0.90 – 0.92) and excellent test-retest correlation ($r= 0.86-0.92$) (McKenna et al., 2006), high sensitivity, specificity, and capacity to measure QOL change over time (Meads et al., 2008). Scores within each domain indicate patients' perception of symptoms, functional ability, and QOL. This questionnaire takes approximately 10 minutes to complete.

Modified Borg Dyspnea Scale (MBDS).

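### The power section says small to medium effects will not reach significance, but a true effect of 0.5 SD of change does so in 44% to 52% of trials, and the SD behind 0.78 is not stated

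*Combined protocol and SAP*

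**What the plan says.** All references are to the combined protocol and SAP.

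- **Procedures, B. Sample, Sample Size and Statistical Power.** For PH-related symptoms and quality of life, two-sided paired tests are assumed "with a significance level of 0.05". The section states that "a sample size of 15 has sufficient power (≥ 0.8) to detect large effect size", which for continuous outcomes is a "standardized mean difference of 0.78 or greater for continuous outcomes". It draws the inference "Therefore, small to medium effect sizes will not be detected as statistically significant in this study". It then says that interpretation will rest on clinical differences and not on significance. Twenty patients are enrolled, attrition of 10-15% is expected, and the minimum final sample is 15.
- **Procedures, E. Data Analysis, Aim 3B.** Pre/post changes in PAHSS and CAMPHOR are tested with McNemar and paired t-tests. The section repeats that "As a pilot study to generate information on preliminary efficacy, we will rely on clinical differences", plans 95% confidence intervals, and says that the point estimates and effect sizes will guide the sample size of a larger study.
- **Procedures, A. Research Design.** Sample size estimates for future randomized trials are named as a purpose of the efficacy exploration.

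No section says which SD standardizes the 0.78, and none gives an expected pre/post correlation. The nearest figure is the test-retest correlation of 0.86-0.92 quoted for CAMPHOR in C. Measurement / Instrumentation.

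**The concern.** Two things look wrong in the continuous part of the power statement.

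First, the inference treats an effect with less than 80% power as one that cannot become significant. A reader who accepts it could take any significant pilot result as evidence of a large effect. With about 15 pairs, a medium true effect will produce such results quite often.

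Second, a paired t-test depends on the mean change divided by the SD of the change. The usual small, medium and large labels refer to the SD of the score itself. The two scales differ by a factor set by the pre/post correlation, and the plan gives neither the scale nor the correlation. If a pilot effect in change-SD units is later used as a between-group effect, the randomized trial could be sized wrongly in either direction.

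**Working it through.** **Inputs.** From Sample Size and Statistical Power: n=15, two-sided paired t-test, alpha 0.05, effect 0.78, 20 enrolled, attrition 10-15%. Expected completers are 20 × 0.85 = 17 to 20 × 0.90 = 18.

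**Step 1: reproduce the plan's figure.** Under the alternative, the test statistic follows a noncentral t distribution with n−1 degrees of freedom and noncentrality d√n, where d is mean change divided by SD of change. For n=15 and d=0.78, the noncentrality is 0.78 × √15 = 3.02 and the critical value is 2.145. Power is 0.802, so the stated figure is right.

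**Step 2: power at smaller true effects, same test.**

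| True effect (SD of change) | n=15 | n=17 | n=18 |
|---|---|---|---|
| 0.2 | 0.11 | 0.12 | 0.13 |
| 0.5 | 0.44 | 0.49 | 0.52 |
| 0.78 | 0.80 | 0.86 | 0.88 |

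A true 0.5 therefore has close to even odds of reaching p<0.05.

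**Step 3: smallest observed effect that is significant.** This is the critical t divided by √n: 2.145/√15 = 0.55, 2.120/√17 = 0.51 and 2.110/√18 = 0.50. All lie well below 0.78.

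**Step 4: what 0.78 means on the score scale.** If the pre and post SDs are equal, SD of change = score SD × √(2(1−r)), where r is the pre/post correlation. So 0.78 SD of change equals 0.78 × √(2(1−r)) score SD. The plan gives no r, so the range below is an assumption for illustration.

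| r | √(2(1−r)) | 0.78 SD of change, in score SD | Power at n=15 for a change of 0.5 score SD |
|---|---|---|---|
| 0.3 | 1.183 | 0.92 | 0.33 |
| 0.5 | 1.000 | 0.78 | 0.44 |
| 0.7 | 0.775 | 0.60 | 0.64 |
| 0.86 | 0.529 | 0.41 | 0.93 |

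The two scales agree only at r=0.5. At that value or below, calling the effect large is fair. At higher r it becomes less so.

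**Step 5: consequence for the later trial (illustration).** Assume a two-arm trial with a t-test, 80% power and two-sided 0.05. The normal approximation per arm is 2(1.96+0.842)²/d², which is 15.7/d². That gives about 26 at 0.78, 44 at 0.60 and 93 at 0.41. The t-test itself needs 27, 45 and 95 per arm. An effect recorded as 0.78 without its unit could stand for any of these.

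**The case against.** The strongest defence is that the sentence is loose power-section shorthand for effects that cannot be detected with the stated power. Read that way it is true on the change-SD scale, since 0.44-0.52 is well below 0.80. It is also nearly true of observed effects: an observed 0.5 is not significant at n=15 or 17 and only just is at n=18. No arithmetic in the power calculation is wrong. The next sentence disclaims reliance on significance, Aim 3B plans confidence intervals, the efficacy aim is exploratory, and no decision rule hangs on these tests. All of that stands and limits the harm. It does not make the sentence correct as written, and it does not supply the missing unit.

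Two stronger readings are tempting, and the documents support neither.

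- **That calling 0.78 large is refuted by the plan's own figures.** A reader might take the CAMPHOR test-retest correlation of 0.86-0.92 as the pre/post correlation and convert 0.78 to 0.41-0.31 score SD. The plan never uses it so. It describes stability without this treatment, whereas here the scores are taken at weeks 1 and 6 during an intervention meant to change them. It is at most an upper guide, it covers CAMPHOR only, and no such figure is given for PAHSS.
- **That pilot results will be misread.** Given the stated reliance on clinical differences and intervals, the text supports only that they could be.

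**Conclusion.** The point holds in a limited form. The power calculation for continuous outcomes is correct, but the conclusion drawn from it is not: at a true 0.5 SD of change the chance of significance is 0.44 at n=15 and 0.49-0.52 at n=17-18, and at 0.2 it is 0.11-0.13. This part rests only on the plan's own inputs.

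The effect-size label is undefined, not shown to be wrong. It depends on a correlation that the plan does not give and may not hold for a highly stable score. The conversion assumes equal SDs before and after.

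Severity is minor to moderate. The main practical consequence lies in carrying pilot effect sizes into a later between-group trial. The sample size and the feasibility and acceptability aims are unaffected. The McNemar part of the power statement is not covered here.

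**What to change.** 1. In Sample Size and Statistical Power, replace the sentence beginning with Therefore by: *Effects smaller than 0.78 SD of change are not detectable with 80% power at n=15; power is 0.44 for 0.5 and 0.11 for 0.2.*
2. In the same place, state that 0.78 is the mean change divided by the SD of the change, and drop or qualify the description of it as large.
3. In Aim 3B, report for each score the mean change in points with its 95% CI, the baseline SD, the SD of change and the pre/post correlation.
4. Base any effect size carried to the later between-group trial on the score SD or on raw points, not on the SD of change.
5. Do not enter 0.86-0.92 as the expected pre/post correlation, since the documents give no basis for that.

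The cost is wording and a few extra summary statistics from data already planned. No patients, visits or instruments are added.
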